#### INSTRUMENT FOR DATA COLLECTION

Data will be collected using a 7-page structured study proforma as included below (Refer to pages 28-34).

### PROCEDURE DETAILS AND DATA COLLECTION TECHNIQUES

#### 1) Before Chest Tube Insertion

In all formally consenting patients who have met the indications for chest tube insertion and participation in this study, the chest tube will be inserted under aseptic techniques. This can be done in the ward at the patient's bedside or in the theatre for post-thoracotomy patients. All chest tube insertion will be performed by the principal investigator or any senior resident doctor in thoracic surgery who has been duly trained to perform this procedure following standard protocols and techniques. The step-by-step guide on how to safely insert a chest tube using the procedural details provided below will be printed out and mastered by all surgeons involved in this study with strict observance of all the required techniques and steps.

As discussed above, a start dose of intravenous third generation cephalosporin antibiotic will be administered prior to the procedure. 1g of Ceftriaxone will be used in this regard in compliance with current practice protocol.

Prior to commencement of the procedure and after formal consent by the patient. The research assistant will be contacted to provide the assigned group for that patient using the computer generated sequence obtained with the WINPEPI software at the beginning of the study.

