# SAMPLING AND RANDOMISATION TECHNIQUES

A block but balanced randomization technique (Unstratified) will be used in determining the use or otherwise of purse-string in the study population. Randomization and intervention assignment into either of the two groups A or B (purse string versus non-purse string) will be determined by grouping labels (A or B) and serialization generated by the soft-ware Winpepi from number 1 to 142 (i.e. Random assignment of 71 in Group A and 71 in Group B).

The generated sequence will be stored on the computer of a blinded research assistant who will be required to inform the team of the next assigned intervention according to the generated sequence, at the time of chest tube insertion for all included and consenting patients. The research assistant will keep record of all assigned labels and ensure all intervention assignment follows the computer-generated sequence in an uninterrupted and reproducible manner.

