# 2) During chest tube insertion

For procedures performed at the patient's bedside, the patient will lie supine or in the cardiac position depending on the diagnosis and clinical condition. The upper limb will be placed under the head for adequate exposure of the safe triangle which is formed by the anterior axillary fold anteriorly, posterior axillary fold posteriorly with the lateral aspect of the sixth rib forming the base. Skin preparation will be done by 10% povidone iodine painting of the anterolateral hemithorax from sternal midline anteriorly to the posterior axillary line and from the clavicle down to the transverse umbilical line. The painting will involve the elbow and finally the axilla will be cleaned. This motion will be carried out thrice to achieve optimal skin sterilization and minimize the risk of contamination.

Thereafter, sterile drapes will be applied to isolate the intercostal space at the mid-axillary line and the surrounding region. The elected site of skin incision is measured using a sterile ruler and marked prior to anaesthesia. Local infiltration of the marked area of skin incision will be done using calculated dose of 2% xylocaine with adrenaline (maximum of 5mg per kg dose). The depth of infiltration should extend to the 5th intercostal space to include the intercostal muscles. After establishing effectiveness of local anaesthesia, a 4cm skin crease incision is then made along the body or lower border of the sixth rib at the mid-axillary line, using a surgical blade and the incision is deepened through the subcutaneous tissue by blunt dissection using a curved number 3 artery forceps or a Kelly forceps. The subcutaneous dissection should create a tunnel extending from the skin incision on the outside to the fifth intercostal space in other to create a superior skin flap. This tunneling is required to create a flap valve-like mechanism aimed at providing an additional method of preventing peritubal leakage after chest tube insertion and development of iatrogenic pneumothorax. The instrument dissection should then be carried through the fifth intercostal space at the upper border of the sixth rib. This is to avoid damage to the subcostal neurovascular structures and also to avoid more pain and haemorrhage.

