At this stage, for patients in whom a purse-string suture has been assigned to be used (Group A), a size 0 polypropylene suture is used in making the horizontal mattress or U-shaped purse string as illustrated in Figure 3 below.

[figure not shown]

FIGURE 3: Illustration of how the purse-string suture is inserted into the thoracostomy wound

To make this horizontal mattress or U-suture placement or purse-string in the thoracostomy wound, the needle of the suture is inserted from point 1, at 1 cm from the wound edge, through the skin and subcutaneous tissue and then exited through point 2, also 1cm from the wound edge. The needle is then re-inserted through the wound about 2cm along the transverse plane which is point 3. The same motion as performed from point 1 to point 2 is done in a reverse pattern from point 3 to point 4. With this, only the free ends of the suture and the part of the suture between point 2 and point 3 lying on the skin surface will be visible while other parts lie within the thoracostomy wound.

This step of U-suture or purse-string placement will be skipped for all patients assigned to Group B. Thereafter, the blunt dissection is continued with the index finger to the level of the parietal pleura which is breached using the tip of the finger or where the pleural is thickened and fibrotic, with the use of the dissecting forceps. The dissecting finger is introduced into the space to assess for pleural adhesions. As indicated above in the exclusion criteria, all patients with pleural adhesions will be excluded from the study. The intrapleural length of the tube will be estimated from the skin incision to the sternal angle. With the aid of the dissecting forceps, this estimated length of the chest tube with blind-ending external part is then advanced apically and posteriorly into the pleural space.

In both groups, the tube is anchored at the anterior and posterior ends of the wound using size 2 silk sutures placed by narrow horizontal mattress suturing or simple interrupted suturing; to secure the chest tube to the chest wall. For patients in Group A, the placed U-suture or purse-string will be knotted once to create air and water tightness (Figure 4) and the loose ends will also be used to anchor the chest tube by tying the loose ends around the chest for a 2 cm length before making a separate knot on the tube to reinforce the previous silk 2 suture anchorages at both wound ends.

[figure not shown]

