#### ETHICAL CONSIDERATION

The study will only be commenced after appropriate approval from the Institutional review board is obtained. Informed consent will be obtained from all the participants of this study after the study has been explained in details to them by a member of the team who will be at least a Senior resident that has been trained on the protocol of the study before the commencement of the study. The aims and objectives of the study will be explained to every potential study participant as well as the method of selection. They will be educated about the method of group assignment and the details of the technique inserting chest tube and the different plans of managing the thoracostomy wound indicating the possible complications of wound infection, wound breakdown, iatrogenic pneumothorax, need for frequent dressings, post-procedural pain and increased analgesic requirements as well as need for chest tube re-insertion. The patients will be reassured of the safety of the chest tube insertion procedure. After group assignment by the research assistant, the patient will be informed of the assigned group and requested to complete the informed consent form to authorize the surgeon to proceed with the procedure as per the protocol described above.

The process of obtaining the informed consent will be individualized, the patient or the guardian will be reassured that the information obtained will be protected and not disseminated. Also, the patient will be informed that the decision to participate or decline participation in the study will not affect the quality of treatment that will be offered to them.

The benefit of the study will be explained to them because it will contribute to the knowledge of in management of patients. The findings may also help surgeons in determining when to use purse strings in management of chest tubes. Also, for patients it will help reduce complications related to chest tube insertion and management.

Suturing with U-Technique versus Un-Reapproximated wound Edges during removal of Closed Thoracostomy-tube drain - A single centre Open-label prospective randomized trial (SUTURE TRIAL)

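### The group is released before the incision although it is first needed at the purse-string step, so the operator makes the unrecorded subcutaneous tunnel knowing the arm

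*Combined protocol and SAP*

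**What the plan says.** Three places in the combined protocol and SAP say when the group becomes known.

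- Section 1) Before Chest Tube Insertion: "Prior to commencement of the procedure and after formal consent by the patient. The research assistant will be contacted to provide the assigned group".
- Sampling and Randomisation Techniques: the assistant tells the team the next assignment "at the time of chest tube insertion for all included and consenting patients". No step within the procedure is named.
- Ethical Consideration: "After group assignment by the research assistant, the patient will be informed of the assigned group and requested to complete the informed consent form".

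Section 2) During chest tube insertion then gives the operative order. First, "a 4cm skin crease incision is then made along the body or lower border of the sixth rib at the mid-axillary line". Next, "The subcutaneous dissection should create a tunnel extending from the skin incision on the outside to the fifth intercostal space", and its purpose is stated: "This tunneling is required to create a flap valve-like mechanism aimed at providing an additional method of preventing peritubal leakage". The same sentence adds iatrogenic pneumothorax as a second thing the tunnel should prevent. Dissection through the fifth intercostal space follows. Only then do the arms part: "At this stage, for patients in whom a purse-string suture has been assigned to be used (Group A"; Group B omits this step. After tube insertion, anchor sutures go in at both wound ends in both groups, "placed by narrow horizontal mattress suturing or simple interrupted suturing".

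**The concern.** In an open-label surgical trial the operator must know the arm at the step that differs, but not before it. Here the arm is known during two steps that are meant to be identical. One of them, the tunnel, acts by the protocol's own account on peri-tubal leakage and pneumothorax. Both appear among the dependent variables under Study Variables and Definition, and acute pneumothorax is the outcome behind the sample size.

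An operator who knows that no purse-string will follow might take more care over the tunnel, or might start the incision at one permitted level rather than the other. If that happened more in one arm, the comparison would mix tunnel technique with closure method. Technique is not among the listed independent variables and is not on the readable proforma, so the adjusted Cox analysis in Data Analysis and Management could neither detect nor correct it.

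**Working it through.** No stated figure has to be reproduced. The point rests on the order of steps and does not depend on the planned 142. The check sets the sections side by side.

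1. **Release of the group.** Section 1 puts it before the procedure starts. Sampling and Randomisation Techniques is compatible with that and names no later step.
2. **Steps between release and divergence.** Section 2 describes site marking, local infiltration, incision, tunnel and dissection through the intercostal space. None of these refers to the arm.
3. **First step that needs the group.** This is purse-string placement or omission. Release could therefore wait until the tunnel is complete without changing any operative step.
4. **Link to outcomes.** Section 2 assigns the tunnel a preventive role for peri-tubal leakage and iatrogenic pneumothorax. Both are compared outcomes.
5. **Room for variation.** Incision length is fixed at 4 cm and the site is measured with a ruler. The incision may lie over the body or the lower border of the sixth rib, so the tunnel's starting point has two permitted levels. Its far end is the fifth intercostal space. No tunnel length or other measure of adequacy is given. What remains open is mainly how well the tunnel is made.
6. **Detectability.** The readable proforma has fields for side, intercostal space, tube size and purse-string use. It has none for incision length, tunnel or anchor technique.
7. **Anchor stitch.** Anchoring comes after the purse-string has been placed or omitted and after the tube is in. The operator knows the arm by then whenever the group is released, so early release does not cause this exposure. The choice between two suturing techniques is a separate, smaller gap.
8. **Consent order.** Section 1 has consent before release. Ethical Consideration has the consent form completed after the patient has been told the group. The two conflict. If the second order stood, delaying the call would achieve nothing, because the patient, often awake under local anaesthesia, would already know the group and could reveal it.

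Exposure can be counted: the incision and tunnel of all 142 planned patients are done with the arm known, and under later release none would be. That is a count of patients exposed, not a measure of bias.

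**The case against.** The case against is substantial. Section 1 requires a printed step-by-step guide, mastered by every surgeon and strictly followed. The incision length is fixed, so a shorter cut in Group B would be a deviation and not a permitted choice. The tunnel runs between two nearby anatomical landmarks, which leaves little scope to extend it. Nothing in the documents shows that operators would behave differently by arm, or in which direction. The Problem Statement reports more pneumothorax and dehiscence with dressing alone, while the literature review reports less pneumothorax without sutures. The trial is also declared open-label: pleural entry, tube placement, anchoring, removal and wound review all take place with the arm known, so later release protects only two steps. Finally, the current consent process depends on disclosing the group before the patient authorises the procedure, so the change is more than a matter of wording.

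Most of this stands, and it limits the point to a cheap improvement. It does not remove it. Unavoidable knowledge from the purse-string step onward is no reason for avoidable knowledge before it, and a guide that is followed to the letter still leaves tunnel execution unmeasured.

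A reader might also infer that early release lets the operator tailor the anchor stitch to the arm. The order of steps does not support that, because anchoring follows divergence under any release time.

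**Conclusion.** The point holds as an avoidable and undetectable route to bias at the incision and tunnel. It does not hold as a demonstrated bias. It rests on the written order of steps being followed and on the readable proforma being complete in this respect.

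Its size cannot be given. At the planned rates, 71 × 0.06 = 4.3 and 71 × 0.012 = 0.9 acute pneumothoraces are expected, and a reader might infer that a single event shifted by technique would decide the trial. That depends on the test: 5 v 0 in 71 per arm gives p = 0.058 by Fisher's exact test but p = 0.023 by uncorrected chi-square, and the plan names Cox regression for complications. A reader might likewise infer an inflated false-positive rate. If technique alone lowered a true 6% to 3% in Group B, rejection would be 12.7% by chi-square but only 4.8% by Fisher, and the halving is an assumption with no source in the documents. Neither calculation is evidence of how large the bias would be.

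**What to change.** 1. In section 1) Before Chest Tube Insertion, state that a non-scrubbed team member contacts the research assistant only after the consent form is signed and after the incision and subcutaneous tunnel are complete, immediately before the purse-string is placed or omitted. The sequence and the assistant stay the same.
2. Name the same moment in Sampling and Randomisation Techniques.
3. Reorder Ethical Consideration so that the patient completes the consent form, covering both arms, before the group is assigned and disclosed. This also resolves its conflict with section 1.
4. As a separate matter not caused by early release, have the operator state which of the two permitted anchor techniques will be used before the group is released, and record it with the incision length on the proforma. Which technique is used is for the investigators.

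The cost is protocol wording, a revised consent sequence, two proforma fields and a brief pause during the procedure, with the assistant on standby. Sample size, significance level and power do not change. The change does not blind later steps, tube removal or outcome assessment, and it does not deal with exclusions for pleural adhesions or tube malposition found after allocation.

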# 2) During chest tube insertion

For procedures performed at the patient's bedside, the patient will lie supine or in the cardiac position depending on the diagnosis and clinical condition. The upper limb will be placed under the head for adequate exposure of the safe triangle which is formed by the anterior axillary fold anteriorly, posterior axillary fold posteriorly with the lateral aspect of the sixth rib forming the base. Skin preparation will be done by 10% povidone iodine painting of the anterolateral hemithorax from sternal midline anteriorly to the posterior axillary line and from the clavicle down to the transverse umbilical line. The painting will involve the elbow and finally the axilla will be cleaned. This motion will be carried out thrice to achieve optimal skin sterilization and minimize the risk of contamination.

Thereafter, sterile drapes will be applied to isolate the intercostal space at the mid-axillary line and the surrounding region. The elected site of skin incision is measured using a sterile ruler and marked prior to anaesthesia. Local infiltration of the marked area of skin incision will be done using calculated dose of 2% xylocaine with adrenaline (maximum of 5mg per kg dose). The depth of infiltration should extend to the 5th intercostal space to include the intercostal muscles. After establishing effectiveness of local anaesthesia, a 4cm skin crease incision is then made along the body or lower border of the sixth rib at the mid-axillary line, using a surgical blade and the incision is deepened through the subcutaneous tissue by blunt dissection using a curved number 3 artery forceps or a Kelly forceps. The subcutaneous dissection should create a tunnel extending from the skin incision on the outside to the fifth intercostal space in other to create a superior skin flap. This tunneling is required to create a flap valve-like mechanism aimed at providing an additional method of preventing peritubal leakage after chest tube insertion and development of iatrogenic pneumothorax. The instrument dissection should then be carried through the fifth intercostal space at the upper border of the sixth rib. This is to avoid damage to the subcostal neurovascular structures and also to avoid more pain and haemorrhage.

At this stage, for patients in whom a purse-string suture has been assigned to be used (Group A), a size 0 polypropylene suture is used in making the horizontal mattress or U-shaped purse string as illustrated in Figure 3 below.

[figure not shown]

FIGURE 3: Illustration of how the purse-string suture is inserted into the thoracostomy wound

To make this horizontal mattress or U-suture placement or purse-string in the thoracostomy wound, the needle of the suture is inserted from point 1, at 1 cm from the wound edge, through the skin and subcutaneous tissue and then exited through point 2, also 1cm from the wound edge. The needle is then re-inserted through the wound about 2cm along the transverse plane which is point 3. The same motion as performed from point 1 to point 2 is done in a reverse pattern from point 3 to point 4. With this, only the free ends of the suture and the part of the suture between point 2 and point 3 lying on the skin surface will be visible while other parts lie within the thoracostomy wound.

This step of U-suture or purse-string placement will be skipped for all patients assigned to Group B. Thereafter, the blunt dissection is continued with the index finger to the level of the parietal pleura which is breached using the tip of the finger or where the pleural is thickened and fibrotic, with the use of the dissecting forceps. The dissecting finger is introduced into the space to assess for pleural adhesions. As indicated above in the exclusion criteria, all patients with pleural adhesions will be excluded from the study. The intrapleural length of the tube will be estimated from the skin incision to the sternal angle. With the aid of the dissecting forceps, this estimated length of the chest tube with blind-ending external part is then advanced apically and posteriorly into the pleural space.

In both groups, the tube is anchored at the anterior and posterior ends of the wound using size 2 silk sutures placed by narrow horizontal mattress suturing or simple interrupted suturing; to secure the chest tube to the chest wall. For patients in Group A, the placed U-suture or purse-string will be knotted once to create air and water tightness (Figure 4) and the loose ends will also be used to anchor the chest tube by tying the loose ends around the chest for a 2 cm length before making a separate knot on the tube to reinforce the previous silk 2 suture anchorages at both wound ends.

[figure not shown]

FIGURE 4: Purse string suture tie around the chest tube to achieve air-water tightness. (4)

[figure not shown]
After this, the tube is clamped and connected to either a flutter-valve bag system or an underwater seal drainage system (9). The site is cleaned and dressing is done using sterile gauze with a light paint of 10% povidone iodine followed by application of a firm plaster.

For large pleural effusions or pneumothorax, the drainage is done gradually in a controlled manner to prevent the development of re-expansion pulmonary oedema.

The details of the technical aspects of the operative procedure of chest tube insertion will be observed as described above in those who have been assigned to either groups that are to have the chest tube inserted as an adjunct to a thoracic surgical procedure (i.e. Operative indication).

# 3) Management of indwelling chest tubes

A chest radiograph will be done immediately after to ascertain the position of the tube and the degree of lung re-expansion. The drainage of the effluent is measured daily and charted; analgesia (combination of 1g oral paracetamol administered every 6hours at 6am, 12 noon, 6pm and 12 midnight; 50mg oral diclofenac sodium administered every 12hours at 10am and 10pm; and 50mg oral tramadol or 5mg oral morphine administered every 6hours at 9am, 3pm, 9pm and 3am) will be instituted for all patients in compliance with current unit analgesic protocol. All patients requiring therapeutic antibiotics (commenced empirically or with culture sensitivity guidance) will have the antibiotics administered according to the posology of the index medication. This category includes post-operative patients who have had chest tube inserted as an adjunct to surgery and those with any other indication for therapeutic antibiotics. All patients will have incentive spirometry (done with the standard threeball incentive spirometer, once every hour) and passive physiotherapy (three times a day). Daily dressing of the chest tube site will be done by the unit doctors during the daily ward rounds using 10% povidone iodine as described above. The pain intensity (pain scores) of the patients will be assessed at regular intervals (atleast twice a day; during morning and evening ward rounds) using the visual analogue scale (VAS), numeric rating scale (NRS) and Categorical verbal rating scale (VRS). Even though the VAS and the NRS have been shown to be superior to the VRS in the assessment of acute post-operative pain, all three will be employed in this study to enhance accuracy of assessment and minimize effect of subjectivity on observed pain scores as depicted in Figure 2 below (45).

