# STUDY VARIABLES AND DEFINITION

The independent variables to be employed for the analysis include:

- Age of the patient
- Sex of the patient
- Presence of specific co-morbidities (Diabetes, Hypertension, Chronic Liver disease, Chronic kidney disease)
- Charleson Comorbidity Index
- History of cigarette smoking and estimated pack years if positive

- Use of steroids and chemotherapeutic agent
- Abnormal Body mass index (Obesity(BMI> 30kg/m^2), Malnutrition(BMI< 18kg/m^2)

The Dependent variables to be employed for the analysis include:

- Presence of severe pain at the chest tube site after chest tube insertion (Average daily pain score after tube insertion > 5 on the Visual Analog Scale and or Numerical Rating Scale)
- Occurrence of tube dislodgement after chest tube insertion
- Occurrence of peri-tubal leakage of fluid after chest tube insertion
- Presence of wound air suck-in after chest tube removal (indicated by presence of air suck-in sound through the wound into the pleural space during quiet and or forced inspiration)
- Occurrence of wound infection after chest tube removal (presence of purulent or offensive wound discharge with or without fever or presence of wound discharge that is microbiologically positive)
- Occurrence of wound dehiscence after chest tube removal
- Occurrence of early (within 7 days) and late pneumothorax (more than 1 week) after chest tube removal confirmed on chest radiography
- Development of raised or elevated thoracostomy wound scars (unsightly scars appearing like hypertrophic scars or keloids) within 3 months of chest tube removal

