# **RESEARCH QUESTIONS**

- What is the difference in the tube-related complication rates after placing a purse-string suture (U suture placement and retention) for thoracostomy wound re-approximation versus non-placement of purse-string at the time of chest tube insertion?
- What is the difference in the early and late complication rates after using a purse-string suture (U suture) for thoracostomy wound re-approximation versus use of only an occlusive adhesiveabsorbent dressing with unreapproximated thoracostomy wound edges; at the time of chest tube removal?
- What is the difference in pain score after using a purse-string suture (U suture) for thoracostomy wound re-approximation versus use of only an occlusive adhesive-absorbent dressing with unreapproximated thoracostomy wound edges; after chest tube removal?
- Is purse-string thoracostomy wound closure associated with more cosmetic complications of thoracostomy scar in the long term than un-reapproximated thoracostomy edges with an occlusive adhesive-absorbent dressing ?

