#### 5) Follow up and treatment adherence

The patients in both groups will be followed up once every month for atleast three consecutive months assessing for evidence of wound infection, pain control and with chest radiography for evidence of pneumothorax. The wound will also be assessed for development of raised or elevated thoracostomy wound scars (unsightly scars appearing like hypertrophic scars or keloids) within 3 months of chest tube removal.

Patients with wound infection will have 10% povidone iodine daily dressing with institution of antibiotic therapy as per unit protocol. All patients with poor pain control (Pain score greater than 5),

involved with in this study, will have their pain control drug regimen escalated as per unit protocol to achieve better pain control.

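### Analgesia reacts to the pain score, includes an unexplained choice of opioid and has no visible place on the form, so equal pain scores cannot be read as equal pain

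*Combined protocol and SAP*

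**What the plan says.** **Regimen.** Procedure details, section 3 (Management of indwelling chest tubes), gives paracetamol, diclofenac and "50mg oral tramadol or 5mg oral morphine administered every 6hours". The combination "will be instituted for all patients in compliance with current unit analgesic protocol". That unit protocol is not reproduced, and the text does not say how the opioid is chosen.

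**Escalation.** Section 5 (Follow up and treatment adherence) sets the trigger: "All patients with poor pain control (Pain score greater than 5". These patients "will have their pain control drug regimen escalated as per unit protocol". The scale, the step taken, and whether one reading or an average counts are not stated.

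**Outcome.** Study Variables and Definition defines severe pain after insertion as "Average daily pain score after tube insertion > 5 on the Visual Analog Scale and or Numerical Rating Scale". Pain is assessed "atleast twice a day; during morning and evening ward rounds" on three scales. The Research Questions also ask, for the period after removal, "What is the difference in pain score after using a purse-string suture (U suture" compared with the dressing alone.

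**Recording.** The Study Proforma has 6AM and 6PM pain scores for days 1 to 10, once after insertion and again after removal. It has fields for steroids, chemotherapy, irradiation and therapeutic antibiotics (type, dose, frequency, duration). None is visible for the analgesic given or for escalation. Ethical Consideration tells patients that they may need more analgesia, yet analgesic use is listed neither as a dependent nor as an independent variable.

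**The concern.** Pain caused by the suture is one of the main arguments in the Problem Statement against the conventional method, and pain has its own research question. Two features of the plan act on the score that answers it.

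- Escalation is triggered by the outcome itself. If the suture hurts more, Group A should receive more drug, and its later scores fall because of that drug.
- The opioid is left open, in a trial where the doctors who dress the wound each day can see whether a purse-string is present.

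If neither is recorded, similar scores in the two groups could mean similar pain, or more pain offset by more drug. The analysis section adjusts for confounders, but analgesic use would not be in the data to be adjusted for or even described.

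**Working it through.** The plan gives no rate, standard deviation, effect size or power for pain. Its sample size of 142 is set on acute pneumothorax and does not bear on this point. The check is therefore a comparison of the rules, followed by an illustration on assumed inputs.

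**1. The two rules side by side**

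| | Severe pain | Escalation |
|---|---|---|
| Cut-off | above 5 | above 5 |
| Score | daily average | not stated |
| Scale | VAS and/or NRS | not stated |
| Period | after insertion | placed under follow-up, but worded for all patients |

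The number is shared; the score, scale and period are not shown to be. The proforma item for major pain after removal has no cut-off.

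**2. How one rule feeds the other.** With two readings x (6AM) and y (6PM), the day counts as severe if (x + y)/2 > 5, that is y > 10 − x. If x = 7, the day counts only if y > 3. A patient who scores 7, is escalated and then scores 3 has (7 + 3)/2 = 5.0 and is not counted. This assumes that a single reading triggers escalation and that the effect is a 4-point fall by evening.

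**3. Direction of the effect of escalation.** Assumptions: 200,000 simulated patients per group; 5 days with 2 readings a day on a 0 to 10 scale; true group means as shown; between-patient SD 1.5; within-patient SD 1; after any reading above 5, all later readings fall by D points. Entries are Group A minus Group B.

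| Measure | Means A v B | D = 0 | D = 1 | D = 2 | D = 3 |
|---|---|---|---|---|---|
| Mean score (points) | 5 v 4 | 0.99 | 0.79 | 0.60 | 0.40 |
| | 4.5 v 3.5 | 0.98 | 0.78 | 0.57 | 0.37 |
| | 6 v 5 | 0.99 | 0.86 | 0.73 | 0.58 |
| Any daily average > 5 (percentage points) | 5 v 4 | 24.4 | 23.6 | 19.5 | 14.0 |
| | 4.5 v 3.5 | 24.7 | 21.3 | 15.8 | 11.0 |
| | 6 v 5 | 17.6 | 22.0 | 23.0 | 19.7 |

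The mean difference shrinks in every row. The yes/no outcome does not always do so. With means 6 v 5 and no escalation, 87.6% of A and 70.0% of B have severe pain. At D = 1 these are 76.9% and 54.9%. A falls by 87.6 − 76.9 = 10.7 points and B by 70.0 − 54.9 = 15.1, so the gap grows by 15.1 − 10.7 = 4.4, from 17.6 to 22.0.

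**4. Direction of the effect of opioid choice.** Further assumptions: one opioid lowers scores by 1 point more than the other, D = 2, means 5 v 4 before that reduction. The difference in the share with any daily average above 5 is:

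- even split in both groups: 15.7 points;
- 80% of A and 20% of B on the stronger-acting option: 6.1 points;
- 20% of A and 80% of B: 25.1 points.

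With no true difference (both means 4.5), the same imbalances alone create a mean difference of about 0.35 points, in either direction.

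**5. What the existing form can still show.** The first reading above 5 is taken before any escalation which that reading triggers. Whether a patient ever has such a reading is therefore not altered by that escalation, and both daily readings are already collected.

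**The case against.** The strongest reply is that one regimen and one escalation rule apply to both groups, so comparing pain under that common policy is a legitimate question. That stands, and the fix adopts it as the main comparison. It does not remove the need to show how much drug each group received.

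Several stronger readings are tempting but not supported:

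- **The comparison is always pulled towards no difference.** This is likely for mean scores. For the yes/no outcome it fails when many patients are near or above 5, and opioid choice has no fixed direction.
- **Staff choose the opioid by group.** The documents do not say so. The unit protocol may contain a selection rule, and randomisation balances the choice unless it depends on group.
- **Nothing can be examined later.** The form keeps both daily readings, so it shows who had a recorded reading above 5. What is lost is the agent given and whether escalation took place.
- **A definite loss of power can be quoted.** Any such figure needs invented pain rates. Hiding the same fraction of patients in both groups would show only the effect of fewer events.
- **Escalation should itself count as severe pain in the main outcome.** If escalation follows single readings and the rule is obeyed, this reduces to any reading above 5. If it is not obeyed, an unblinded decision enters the endpoint.

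Two limits also stand. The escalation rule reaches the indwelling period only through its wording for all patients. A figure is missing near the drug-history item of the proforma, so the analgesic field is not visible rather than proven absent.

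**Conclusion.** The point holds as one of interpretation. Analgesia is driven by the outcome, given open label and apparently not recorded, so a finding of equal pain scores would not establish equal pain. Escalation most likely dilutes the difference in mean score: under the assumed inputs a true difference of about 1 point falls to between 0.37 and 0.86. Its effect on the severe-pain outcome can go either way, and opioid choice that depends on group could mask, exaggerate or create a difference. These sizes are illustrations and rest wholly on the assumed means, SDs and drug effects; they are not estimates for this trial. The acute pneumothorax comparison, on which the trial is sized, is untouched. This is a cheap improvement to the trial's own pain question, not a flaw in the whole design.

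**What to change.** 1. Add two fields to the proforma, in both the post-insertion and post-removal panels: the opioid given, and any escalation with its date. Add them before or during data collection, since unrecorded use may not be recoverable. Dates matter because escalation while the tube is in place can carry over into the readings after removal.
2. Report analgesic use and escalation by group beside the pain results.
3. State that the main pain comparison is made regardless of escalation.
4. Add a sensitivity analysis that counts a patient as having severe pain at the first single 6AM or 6PM reading above 5. It needs no new data. It measures peak rather than average pain, does not remove the effect of the initial opioid choice, and could be affected by an earlier escalation prompted by a reading not on the form.
5. Reconcile Study Variables and Definition with sections 3 and 5 of the procedure details: which score (single or average), which scale and which period trigger escalation, and how the opioid is chosen independently of group. The choice of agent and the escalation steps remain with the clinical team.

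The cost is two form fields, one extra analysis and a short clarification of the text.
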